## Specific Aims and Hypotheses

### Specific Aims and Hypotheses

We hypothesize that treatment with levodopa (L-DOPA) will improve depressive symptoms in LLD by enhancing striatal dopamine release and improving cognitive/motor slowing. In the R33 Phase, 90 adults aged > 60 years with (1) a DSM 5 depressive disorder, (2) significant depressive symptoms (CES-D > 10), and (3) decreased processing speed (0.5 SD below age-adjusted norms on the Digit Symbol Test or Trails A) or decreased gait speed (average walking speed over 15' course < 1m/s) will be receive 8 weeks of treatment with LDOPA 450mg. Subjects will be tested for engagement of molecular target by determining whether subacute (8 week) treatment with L-DOPA displaces [C]-raclopride on positron emission tomography (PET).

R33 Phase.

Aim 1: To determine whether L-DOPA improves depressive symptoms in older adults.

Hypothesis 1: Compared to placebo, L-DOPA administration will result in greater improvements in depressive symptoms (as measured by HRSD scores).

Hypothesis 2: Greater post-L-DOPA decreases in [C]-raclopride BP and increases in processing/gait speed will be associated with greater depressive symptom improvement.

Exploratory aims: To explore the role of inflammatory markers and Catechol-O-methyl-transferase (COMT) genotype in moderating L-DOPA induced changes in slowing and depressive symptoms.

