6. Other neuropsychological measures completed at baseline include trained study rater (BA, RN, SW) assessment of episodic memory functioning using the Wechsler Memory Scale Logical Memory Test I & II (153). Inclusion of this test will allow us to identify deficits in episodic memory functioning consistent with a classification of amnesic mild cognitive impairment (aMCI) (7). Executive function will be assessed via the NIH-EXAMINER battery designed to assess executive functions reliably, comprehensively, and efficiently (154-155). This battery examines working memory, inhibition, set shifting, fluency, insight, planning, social cognition and behavior. Confirmatory factor analysis supports both a one-factor model and

a three- factor model, and these models formed the basis for an Executive Composite score and subscales scores for Working Memory, Cognitive Control, and Fluency.

7. Domains of function assessed by trained study raters (BA, RN, SW) at baseline include: the Short Physical Performance Battery (SPPB) (156), a performance measure of gait, balance, and lower extremity strength sensitive to meaningful change. The 36-item self-report World Health Organization Disability Assessment Schedule 2.0 (WHODAS2) provides a global measure of disability and 7 domain-specific scores based on the conceptual framework of the International Classification of Functioning, Disability, and Health (ICF) (157). The self-report 38-item Measure of Everyday Cognition (ECog) is adapted from an informant-report version and measures impairment and change in domains of everyday/real-world functioning relevant to 7 specific neuropsychological domains (158). The Falls Efficacy Scale-International will assess subjects' fear of falling weekly using a 16-item scale rating respondents' confidence (1 not at all concerned—4 very concerned) in doing daily tasks without falling (159-160).

8. Finally, aliquots of peripheral blood will be frozen for subsequent DNA isolation and determination of interleukin-6 (IL-6) and catechol-O-methyl-transferase (COMT) genotype. These genotypes will be analyzed in exploratory analyses to determine their effects on baseline dopamine functioning and response to L-DOPA.

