Analyses for Aim 3: Aim 3.1: To determine whether L-DOPA administration results in greater improvements in depressive symptoms on the HRSD, a longitudinal mixed effects model will be used to analyze group differences using SAS Proc Mixed Version 9.3. The change in 24-item HRSD from baseline will be analyzed as a function of time, treatment group, the interaction between time and treatment, and baseline HRSD. Contrasts of mean difference in HRSD at each week will be formed and tested. Aim 3.2: To determine whether greater increases in processing and gait speed are associated with greater HRSD improvement, change scores from baseline to 8 weeks will be calculated for both processing and gait speed. Pearson correlation among all change scores, including change in HRSD will be examined, and two-sample t-tests will be used to assess treatment group differences. Multivariate linear regression models will be fit with change in HRSD as the outcome predicted by treatment, processing and gait speed change scores, and baseline values of processing and gait speed.

Exploratory aims: Inflammatory markers and COMT genotype will be tested as moderators of the L-DOPA effect on HRSD change by including their interactions with treatment in the Aim 3 analyses.

Power analysis: Aim 3.1: With N=45 per treatment group, and assuming a drop out of 15%, using two-sided test with $\alpha=0.05$, we have >80% power to detect treatment group differences with ES = 0.60 or greater. Given expected SD=5 points based on similar previously conducted studies in the LLDRRC, this ES would correspond to a change in HRSD of 3 points, which is smaller than the 4 point change considered meaningful. Aim 3.2: With N=90, assuming a drop out of 15%, we would be able to detect correlations >0.31. Thus, we have adequate power to detect a moderate to large correlations between change in HRSD and change in processing and gait speed.

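### Moderation of slowing, half of the protocol's exploratory aim, has no planned analysis, and the Aim 3.2 version of the HRSD moderator test leaves out any moderation that runs through speed

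*SAP*

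**What the plan says.** The protocol (Specific Aims and Hypotheses, exploratory aims) sets out to explore the role of inflammatory markers and COMT genotype "in moderating L-DOPA induced changes in slowing and depressive symptoms". Two outcomes are named. For the IL-6 and COMT genotypes, Study Procedures (Evaluation, item 8) adds: "These genotypes will be analyzed in exploratory analyses to determine their effects on baseline dopamine functioning and response to L-DOPA".

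Of inflammatory markers and COMT genotype, the SAP's exploratory paragraph says that they "will be tested as moderators of the L-DOPA effect on HRSD change by including their interactions with treatment in the Aim 3 analyses". One outcome is named, and IL-6 genotype is not listed.

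The SAP has two Aim 3 analyses of HRSD:

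- **Aim 3.1**, a mixed model: "The change in 24-item HRSD from baseline will be analyzed as a function of time, treatment group, the interaction between time and treatment", plus baseline HRSD. It has no speed covariates.
- **Aim 3.2**, in which "change scores from baseline to 8 weeks will be calculated for both processing and gait speed" and then "Multivariate linear regression models will be fit with change in HRSD as the outcome predicted by treatment, processing and gait speed change scores", plus baseline speed. Alongside the correlations, "two-sample t-tests will be used to assess treatment group differences".

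The protocol's central hypothesis is that L-DOPA improves depression "by enhancing striatal dopamine release and improving cognitive/motor slowing". Study Procedures (Evaluation, item 5) justifies the inflammatory markers by their possible effect on dopaminergic function, which lies upstream of speed.

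**The concern.** There are two separate problems.

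First, no SAP model has processing or gait speed as its outcome together with a marker-by-treatment term. The slowing half of the exploratory aim would end the trial without a pre-planned answer, in a study built around slowing as the mechanism.

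Second, read literally, the SAP sentence adds the moderator term to the Aim 3.2 regression as well. That model conditions on change in speed measured after randomisation, and speed change is the proposed route from L-DOPA to mood. A marker-by-treatment coefficient beside it answers a narrower question: does the marker change the part of the L-DOPA effect that does not pass through speed? Participants compared at equal speed change are also no longer protected by randomisation.

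The plan would therefore yield two HRSD moderator results with different meanings under one label, and none for slowing. The protocol's rationale section hopes that such markers will help to identify who benefits, so a misread null would matter.

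**Working it through.** The documents give no sample size, power or effect size for the moderator analyses, so there is no planned figure to reproduce. The check has four steps.

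**1. Outcomes named against analyses planned**

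| Question in the protocol aim | SAP analysis |
|---|---|
| Does the marker moderate the effect on depressive symptoms? | Yes: marker by treatment in Aim 3.1 and Aim 3.2 |
| Does the marker moderate the effect on slowing? | None; at most, t-tests of speed change by arm, without a marker |

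**2. What the interaction estimates in each model**

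Let T be treatment, W the marker (SD 1), and S1 and S2 the processing- and gait-speed changes. Suppose each S contains m·T·W, and HRSD change equals b·S1 + b·S2 + d·T·W + noise.

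- Without speed covariates (as in Aim 3.1), the T·W coefficient is 2·b·m + d, the total moderation.
- With S1 and S2 as covariates (as in Aim 3.2), it is d alone.

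With m = 1.0, b = -1.5 and d = 0, the total is 2 × (-1.5) × 1.0 = -3.0 HRSD points, and the Aim 3.2 coefficient is 0.

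**3. Simulation**

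N = 76 comes from the SAP: 90 × 0.85 = 76.5. There were 4,000 replicates fitted by ordinary least squares, with two-sided alpha 0.05 (SAP). The effect sizes are assumptions: a treatment main effect of 0.5 on each speed change, speed noise SD 1 and HRSD noise SD 4. A single HRSD change score stands in for the Week 8 contrast of the mixed model. Cells show the mean interaction and the rejection rate.

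| Scenario | HRSD, no speed covariates | HRSD, both speed changes as covariates | Speed change as outcome (absent from the SAP) |
|---|---|---|---|
| All through speed (m = 1.0) | -3.0, 78% | 0.0, 5% | 1.0, 98% |
| Same, speed reliability 0.7 | -3.0, 78% | -1.2, 17% | 1.0, 89% |
| All through speed (m = 0.5) | -1.5, 28% | 0.0, 5% | 0.5, 56% |
| Half through speed (m = 0.5, d = -1.5) | -3.0, 78% | -1.5, 31% | 0.5, 56% |
| None through speed (d = -3) | -3.0, 79% | -3.0, 86.5% | 0.0, 5% |
| Marker alters slowing, slowing does not alter HRSD (m = 0.5, b = 0) | 0.0, 5% | 0.0, 5% | 0.5, 55% |

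The last row bears on the first problem. If a marker changes the effect on slowing without a knock-on effect on mood, only the model that the SAP lacks can show it.

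**4. Limits of power and timing**

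- *Power.* Take a marker split 50/50, 38 per arm and the SAP's SD of 5. The standard error of the interaction is 5 × √(2/19 + 2/19) = 2.29. The interaction detectable with 80% power is 2.29 × (1.96 + 0.84) = 6.4 points. Power for a 3-point interaction is Φ(3/2.29 - 1.96), about 26%.
- *Timing.* The sentence does not say whether the Aim 3.1 term is crossed with time. If it is not, one coefficient averages over the weekly visits. Moderation proportional to daily dose (150 mg, then 300 mg, then 450 mg for six weeks) gives an equal-weight average of (1/3 + 2/3 + 6)/8 = 87.5% of the Week 8 value. A linear build-up from Week 1 to Week 8 gives 4.5/8 = 56%. Both shapes are assumptions.

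**The case against.** The strongest reply is that nothing essential on HRSD is lost. The Aim 3.1 model has no speed covariates, so the same sentence already delivers moderation of the total HRSD effect. The Aim 3.2 term is an additional estimate with a legitimate meaning, provided that it is labelled. This stands. It limits the second problem to interpretation and labelling.

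Three stronger readings are tempting, and the documents do not support them:

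- **That slowing is never tested.** The Aim 3.2 change scores and t-tests can compare processing and gait speed between arms. Only *moderation* of slowing is unplanned.
- **That a true moderator would be reported as null.** This needs all of the moderation to run through speed, and speed to be measured without error. Otherwise the loss is partial, or nil. At realistic interaction sizes a null is likely even in the right model, because power is low.
- **That the mixed model forces one moderation effect over all weeks and dilutes it to about half.** The SAP's wording leaves room for a marker-by-treatment-by-time term, and the model already has time by treatment and weekly contrasts. The text is ambiguous, not wrong, and no passage supports a linear build-up.

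It is also fair to say that the formal exploratory aim lists only inflammatory markers and COMT, as the SAP does. IL-6 genotype comes from the procedures section, so its omission is minor.

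**Conclusion.** The point holds in two parts.

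The mismatch of outcomes follows from the two texts and needs no assumption: the protocol names moderation of slowing, and the SAP plans none.

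The Aim 3.2 part follows from the model's covariates. There the interaction excludes any moderation that passes through speed. How much that removes depends on how much runs through speed and how well speed is measured. The simulated range is from all of a 3-point interaction to none of it, under assumed effect sizes.

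The analyses are exploratory and carry no power claim, and the primary HRSD comparison is untouched. The plan should still be amended, because the repair is small and otherwise the trial cannot answer its own exploratory question as planned.

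**What to change.** Rewrite the SAP's exploratory paragraph so that it does the following:

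- **(a)** Adds exploratory models with processing speed and gait speed as outcomes, each with a marker-by-treatment interaction. The protocol already collects both at baseline and Weeks 1, 2, 5 and 8 (Study Procedures, Assessments).
- **(b)** Takes HRSD moderation from the Aim 3.1 model, with marker by treatment by time (and the lower-order terms), and reports the Week 8 contrast.
- **(c)** Does not use the Aim 3.2 regression to test moderation of the L-DOPA effect, or else labels any such term as moderation of the direct effect only, meaning the part not passing through speed.
- **(d)** Adds IL-6 genotype to the listed moderators, in line with Study Procedures (Evaluation, item 8).

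All of these should be labelled exploratory and reported as estimates with confidence intervals. The cost is SAP wording and a few more model runs, with no new data collection. The downside is more exploratory tests with low power for interactions at about 76 completers, which the SAP should state.

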### Assessments

21. Subjects are expected to have a screening/evaluation visit, pre-treatment PET/MRI scanning day(s) (for those receiving imaging), and weekly visits from Week 0-8.

22. The following measures will be collected weekly throughout the study: 24-item HRSD, CGI Severity and Improvement, Structured Pill Count Interview, Unified Parkinson's Disease Rating Scale (UPDRS) (questions 32 and 33 will be used in this study to assess the duration and disability of dyskinesias caused by L-DOPA), Treatment Emergent Side Effect Scale, and Inventory of Depressive Symptoms—Self Report (IDS-SR).

23. In addition, baseline processing and gait speed assessments will be repeated after **Weeks 1, 2, 5, and 8** at 1pm to control for time of day effects and the duration since the last morning L-DOPA dose (anticipated to be 4 hours). Processing speed will be assessed using the Digit Symbol test from the Wechsler Adult Intelligence Scale-III (WAISIII) (119) and the Pattern and Letter Comparison tests (120). These tests are all reliable and valid, with moderate to high loadings on the latent speed factor. A latent factor (and subsequent factor score) will be extracted from the 3-test battery pre- and post-treatment and used as the main outcome in the R61. By extracting a latent factor and factor loadings we will utilize a more pure measure of processing speed than if we used the raw scores from an individual test or a sum total score from the three raw scores combined (121-124).

24. Gait will be assessed as both a single and dual task (ST, DT) on a Gaitrite walkway system in the LLDC. For the ST, patients are instructed to walk at their usual or normal speed over the walking course. For the DT, patients are instructed to walk at their usual pace while simultaneously verbally listing as many animals as possible (fluency DT). In addition, a counting DT will be used in which patients are instructed to walk at their usual pace while simultaneously performing serial subtractions by threes starting at 100 (125). Patients will start and end at a point 2 meters from beginning of the course to eliminate acceleration and deceleration effects. Each ST and DT will be assessed two times with the average used in the analyses.

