Statistical Analysis Plan

Targeting Dopaminergic Mechanisms of Slowing to Improve Late-Life Depression

IRB #7733

NCT #03761030

Date: 07/24/15

Overview: All variables at all time points will be examined for illegitimate values, outliers, and inconsistencies. The distribution of demographic variables and baseline clinical characteristics will be examined and described across the two randomized patient groups (N=45 each) in terms of means, standard deviations, proportions, and 95% confidence intervals. Indications of inequality between groups in specific features (despite randomization) will trigger examination of whether differences in primary outcome measures can be attributed to an imbalance in group assignment. Intent-to-treat will be used for analyses including all participants who are randomized and have at least one post-baseline HRSD score. Tests will be two-sided and statistical significance determined at p-value < 0.05.

Missing data: We will make every effort to obtain all data. The longitudinal mixed modeling described below is valid if missing data are missing at random (MAR). MAR assumptions cannot be verified. A 2010 national expert panel (166) recommended sensitivity analyses for the impact of missing data via pattern mixture models (167), which we will conduct (e.g., by investigating robustness of results to perturbations of assumed values for missing data within clinically plausible ranges).

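### The SAP's power of over 80% at ES 0.60 does not follow from its stated inputs once the 15% dropout is applied; a two-sample calculation gives about 73–74%

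*SAP*

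**What the plan says.** The Aim 3.1 power statement in the SAP begins "With N=45 per treatment group, and assuming a drop out of 15"%, specifies a two-sided test at alpha 0.05, and concludes "we have >80% power to detect treatment group differences with ES = 0.60 or greater". It turns the effect size into points: "Given expected SD=5 points based on similar previously conducted studies in the LLDRRC", 0.60 corresponds to 3 HRSD points, which it notes is below the 4 points it regards as meaningful.

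Three other places bear on the calculation:

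- **Number randomised.** The SAP Overview says baseline characteristics will be "described across the two randomized patient groups (N=45 each"). So 45 is the number before dropout, not the number left after it.
- **Analysis set.** The Overview also says "Intent-to-treat will be used for analyses including all participants who are randomized and have at least one post-baseline HRSD score". The Protocol (Assessments) adds "The following measures will be collected weekly throughout the study: 24-item HRSD". A participant who leaves early therefore still contributes data.
- **Model.** Change in HRSD is modelled as a "function of time, treatment group, the interaction between time and treatment, and baseline HRSD", and "Contrasts of mean difference in HRSD at each week will be formed and tested".

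The SAP names no formula for the power figure. It gives no within-subject correlation and no correlation between baseline and outcome.

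**The concern.** The sentence presents the power as already allowing for 15% dropout. An effect size of 0.60 with 45 per arm is almost exactly the textbook two-sample design for 80% power with nobody lost, so there is little room for dropout in it.

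This is the only power statement for the primary comparison in the two documents. A reader of a null result would take the chance of missing a true 3-point difference to be under 20%. If dropout was not in fact applied, that chance is higher on the stated inputs, and the detectable difference is larger than stated.

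**Working it through.** **Inputs (all from the SAP).** 45 randomised per arm; 15% dropout, so 45 × 0.85 = 38.25, or 38–39 per arm; two-sided alpha 0.05; difference 3 points and SD 5, so d = 3/5 = 0.60.

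**Formula.** For a two-sample t-test with n per arm, the noncentrality is λ = d√(n/2) on 2n − 2 degrees of freedom. Power is the probability that a noncentral t variable exceeds the two-sided 5% critical value. The normal approximation is Φ(λ − 1.96).

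**Results at d = 0.60**

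| n per arm | λ | Power (t) | Power (normal) |
|---|---|---|---|
| 45 (no dropout) | 0.60 × √22.5 = 2.846 | 80.4% | 81.2% |
| 44 | 0.60 × √22 = 2.814 | 79.5% | – |
| 39 | 0.60 × √19.5 = 2.650 | 74.4% | 75.5% |
| 38 | 0.60 × √19 = 2.615 | 73.3% | 74.4% |

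The SAP's figure is reproduced in the first row only. A one-sided test at 38 per arm would give 82.8%, but the SAP specifies two-sided.

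**Size of the gap**

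- 80% power at d = 0.60 needs 44.6 evaluable per arm by t, or 43.6 by the normal approximation. From 45 randomised, that leaves room for 0.9% or 3.1% dropout.
- At 38 per arm, 80% power needs d = 0.651, and 0.651 × 5 = 3.3 points. At 39 per arm it needs d = 0.643 (3.2 points).
- Type II error at 3 points is 100 − 74.4 = 25.6% to 100 − 73.3 = 26.7%.
- At 4 points (d = 4/5 = 0.80), power is 93.1% at 38 per arm.

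**What the planned model could add.** The SAP gives none of the correlations below; they are assumptions, shown as ranges.

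1. *Baseline covariate, 38 completers per arm, SD 5 taken as unadjusted.* The adjusted SD would have to be 3/0.651 = 4.61. The variance ratio is (0.60/0.651)² = 0.849, so the baseline correlation must be √(1 − 0.849) = 0.39. Power at correlations of 0.2, 0.3, 0.4 and 0.5 is 75.0%, 77.2%, 80.4% and 84.6%.
2. *Partial data from dropouts, Week 8 contrast, no baseline gain.* Assume eight weekly visits, with the last visit of those who drop out spread evenly over Weeks 1–7. Power is 75.3% under AR(1) with correlation 0.8. Under compound symmetry of 0.5, 0.6, 0.7, 0.8 and 0.9 it is 76.1%, 76.9%, 77.7%, 78.5% and 79.4%. A baseline correlation of about 0.12–0.34 would then bring it to 80%.
3. *Constant effect averaged over Weeks 3–8.* Under compound symmetry of 0.5–0.9, power is 83–95% with partial data and 77–92% with 38 completers per arm.

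**A hint at the cause, as inference only.** Aim 3.2 says correlations above 0.31 are detectable with N = 90 and the same dropout. At an assumed 80% power, the detectable correlation at n = 76 is 0.317 (Fisher z) or 0.310 (t-based), against 0.292 or 0.286 at n = 90. So 0.31 fits dropout having been applied there, while the Aim 3.1 figure fits dropout not applied. Aim 3.2 states no power level, so this is weak evidence and nothing here depends on it.

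**The case against.** The strongest reply is that a completer t-test is not the planned analysis. The model is longitudinal, adjusts for baseline HRSD, and keeps everyone with one post-baseline score. Each feature can add power, and some readings put it above 80%: an effect averaged over several weeks, a baseline correlation near 0.4, or a weaker one combined with partial data. Choosing the two-sample test is itself an assumption that the SAP does not state.

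This stands in part. It rules out saying that the claim is false, and it makes 73–74% a conservative figure. It does not support the sentence, because the reader would have to supply every input that produces the gain. Partial data alone do not bring a Week 8 contrast to 80% in any of the cases examined, and the SAP describes contrasts at each week without tying 0.60 to any week or average.

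Two further replies are fair. The point that losing one participant per arm takes power below 80% is a threshold effect; the more useful measure is the shift in detectable effect from 0.60 to 0.65. And the practical stakes are modest, because the comparison with 4 points survives.

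**Conclusion.** The concern holds. Power above 80% at ES 0.60 after 15% dropout cannot be reproduced from the inputs the SAP states. As a two-sample calculation the figure fits 45 per arm with no dropout; with the dropout applied, power is 6–7 percentage points below 80%, and the difference detectable with 80% power rises from 3 to 3.3 points. For a Week 8 contrast that uses partial data under the assumed correlations, the shortfall narrows to about 1–5 points (type II error about 21–25%). With enough baseline correlation, or with an effect averaged over weeks, it may disappear. Which of these applies depends on quantities the SAP does not report.

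The two-sample figures rest only on the SAP's own numbers and the choice of that test. The SAP's conclusion that the detectable difference lies below 4 points is unaffected. The statement should be corrected because it is the stated basis for the primary comparison, but the design is not called into question.

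**What to change.** Change the Aim 3.1 power statement in one of two ways:

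- **Restate it.** With 38 per arm after 15% dropout, an unadjusted two-sample completer calculation, which is conservative for the planned mixed model, gives about 73% power at ES 0.60 and 80% power at ES 0.65 (3.3 points at SD 5).
- **Or keep a higher figure and state what produces it.** Give the time point or average to which ES 0.60 refers, the within-subject correlation, the correlation between baseline and outcome, and whether SD 5 is before or after baseline adjustment.

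Separately, and not as evidence for this point, the Protocol (Description of Subject Population, Sample #1) requires 68 completers from 90 enrolled, a loss of 1 − 68/90 = 24%. Reconcile this with the SAP's 15%, or say why the two differ.

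The cost is one or two sentences in the SAP and one entry or explanatory line in the Protocol. Sample size, conduct and analysis stay as they are.
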